8.2 Safety Endpoints

- i. Primary safety endpoint:
 - Cesarean delivery performed for primary indication of nonreassuring fetal status
- ii. Secondary safety endpoints:
 - Measures of neonatal morbidity
 - a. Stillbirth or neonatal death
 - b. Umbilical cord arterial blood pH less than 7.0 or base deficit greater than 12 mmol/L; or cord venous blood pH less than 7.0 or base deficit greater than 12 mmol/L when umbilical artery values are not available.
 - c. Neonatal Apgar score at five minutes of life of less than 3
 - d. Admission to Neonatal Intensive Care Unit (NICU)

- i. Length of stay in NICU, if applicable
- e. Additional morbidities: severe respiratory distress requiring cardiorespiratory support and/or ventilation (intubation, continuous positive airway pressure, high-flow nasal cannula) for more than 12 hours, major birth injury (brachial plexus injury, bone fractures, other neurologic injury, facial nerve injury), neonatal encephalopathy, neonatal seizure, need for hypothermic treatment (cooling), and neonatal sepsis (positive blood, urine, or cerebrospinal fluid culture; or in the absence of positive culture(s), clinical evidence of cardiovascular collapse or an unequivocal X-ray confirming infection).

9.0 Procedures Involved

- 9.1 Study Design: We propose a double blind randomized clinical trial:
 - i. Recruitment: Patients meeting eligibility criteria (as listed above) will be approached for potential recruitment, with the assent of their primary obstetric physician or midwife, once their hospital admission for a trial of labor has been confirmed.
 - Intervention: After informed consent is obtained, subjects will be ii. enrolled if and when their primary obstetric physician or midwife determines that oxytocin is to be initiated for labor augmentation. One group, labeled as LDOR, will undergo our primary institutional protocol (Protocol #12.0053) with a starting oxytocin concentration rate of 2mU/min that can be increased at increments of 2mU/min, as per the discretion of each individual's primary obstetric physician or midwife. The other group, labeled as HDOR, will undergo our supplemental institutional protocol for Active Management of Labor (Protocol #12.005m Appendix A) with a starting oxytocin concentration rate of 6mU/min that can be increased at increments of 6mU/min, as per the discretion of each individual's primary obstetric physician or midwife. The solutions used in the two groups will appear identical and volume infusion rates (2mL/hour) will be identical to ensure double blinding. The sole difference between the two groups will be the oxytocin concentration, with 30U oxytocin in 500mL of 0.9% normal saline (NS) in the LDOR group and 90U oxytocin in 500mL of 0.9% NS in the HDOR group. Once a patient is enrolled, randomized, and in receipt of the assigned intervention, further clinical management will be left to the discretion of each patient's primary obstetric physician or midwife. Each subject will have a unique drug code, which will remain with her for the trial duration, and

Page 8 of 23 Revised Template: November 10, 2014

- drug preparations will be labeled with the same unique code by the pharmacy.
- iii. Randomization: Fixed allocation procedure will assign the interventions to subjects with equal probability using a blocked randomization scheme without stratification. To maintain a double blind design, the NMH Investigational Pharmacy will carry out the randomization and preparation of oxytocin solutions according to the random assignment so that neither the patients and their care providers nor the investigators will know the identity of the intervention assignment.
- 9.2 Emergency unblinding procedures will be established so that patient safety is not jeopardized. Once a patient is enrolled, randomized, and in receipt of the assigned intervention, further clinical management will be left to the discretion of each subject's primary obstetric physician or midwife.
- 9.3 Procedures to lessen the probability or magnitude of risks:
 - Continuous external fetal monitoring (EFM) will be required during oxytocin infusion for both treatment groups. As per established institutional clinical protocol (Protocol #12.0053), each subject will be monitored closely during oxytocin infusion. Specifically, in latent labor, the subject's clinical nurse will assess and document contraction intensity, duration and frequency as well as fetal heart rate (FHR) baseline, variability, and any periodic change every 30 minutes and with each oxytocin rate change. In active labor and stage 2 of labor, the subject's clinical nurse will assess and document contraction intensity, duration and frequency as well as FHR baseline, variability, and any periodic change every 15 minutes and with each oxytocin rate change. If a tachysystole contraction pattern (defined as more than 5 contractions in 10 minutes, averaged over a 30-minute window) is identified, the oxytocin infusion will be decreased to the previous milliunit rate setting and reevaluated in 15 minutes. If a tachysystole pattern persists at this first 15 minute-mark, the oxytocin infusion will be decreased by one-half the current rate, and reevaluated again in 15 minutes. If a tachysystole pattern persists at this second 15-minute mark, the oxytocin infusion will be discontinued. The oxytocin infusion may then be restarted if the FHR is normal, and contraction frequency, intensity, and duration are normal at the initial start dose. If a FHR pattern is deemed to be Category 2, the subject's primary obstetric physician or midwife will be required to visualize the EFM recording and will determine further oxytocin titration. For a prolonged deceleration (defined as a decrease in FHR from baseline lasting more than two minutes), the oxytocin infusion will be discontinued. If a FHR pattern is deemed to be Category 3 (absent baseline FHR variability with any of the following: recurrent late decelerations, recurrent variable decelerations, bradycardia, or sinusoidal pattern), the oxytocin infusion will be discontinued, and the primary obstetric physician or

- midwife will be notified. If the oxytocin has been discontinued for a Category 2 or 3 pattern, the oxytocin may be restarted per the order of the primary obstetric physician or midwife when the FHR tracing has returned to a Category 1 or reassuring Category 2 tracing at no more than one-half the dose that preceded the discontinuation. Maternal pulse, respirations, and blood pressure will be evaluated and recorded hourly or more frequently if necessary based on patient status. Maternal temperature will be evaluated every 2 hours with intact membranes, and every hour following rupture of membranes.
- ii. Subjects in the LDOR group will receive standard oxytocin infusion according to the established NMH Clinical Protocol for Induction and Augmentation of Labor, Protocol #12.0053 (protocol is attached). In accordance with this protocol, the oxytocin infusion will be started at a rate of 2 mU/min (to maintain blinded design, pump rate will be "set" at 2 mL/hr with a concentration of 30 U oxytocin in 500mL of 0.9% NS) for the subjects in the LDOR group. The rate will be increased by 2 mU/min no more frequently than every 15-30 minutes until a labor pattern with uterine contractions every 2-3 minutes of moderate to strong intensity is established. Subjects in the HDOR group will receive oxytocin infusion according to the established supplemental NMH Clinical Protocol for Induction and Augmentation of Labor, Protocol #12.0053 (Appendix A – Active Management of Labor). In accordance with this supplemental protocol, the oxytocin infusion will be started at 6 mU/min (to maintain blinded design, pump rate will be "set" at 2 mL/hr with oxytocin concentration of 90 U oxytocin in 500mL of 0.9% NS) for the subjects in the HDOR group. The rate will be increased by 6mU/min (to maintain blinded design, pump rate will be "increased" by 2 mL/hr with oxytocin concentration of 90 U oxytocin in 500mL of 0.9% NS) until a labor pattern with uterine contractions every 2-3 minutes of moderate to strong intensity is established.
- iii. The medical record of each subject's hospital stay will be reviewed and used to collect data. A data collection form will be utilized by the study investigators to extract data from each subject's medical record ('data collection' form attached)
- 9.4 Clinical data that are pertinent to the study endpoints during the hospital stay will be collected (see 'data collection form'). There will be no long-term follow-up; the study period begins at randomization and ends with discharge from hospital following delivery. Data will be collected only up until time of each subject's hospital discharge.
- 9.5 Not applicable

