3.3 Special Populations

- *i.* Adults unable to consent: Subjects who are unable to consent will not be included in our study.
- ii. Individuals who are not yet adults (infants, children, teenagers): Our study will only include subjects who are adults, and are 18 -45 years of age.
- *iii.* Pregnant women: This population will be included since our study is focused specifically on the obstetric population.
- iv. Prisoners: This is not applicable to our study; we will recruit solely from the population of pregnant women who deliver at Northwestern Memorial Hospital – Prentice Women's Hospital.
- **4.0 Study-Wide Number of Subjects** Not applicable
- **5.0 Study-Wide Recruitment Methods** Not applicable as this is a single-center clinical trial
- **6.0** Multi-Site Research Not applicable as this is a single-center clinical trial

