7.0 Study Timelines

7.1 Timelines

- After informed consent is obtained, subjects will be enrolled in the study if and when their primary obstetric physician or midwife determines that oxytocin needs to be initiated for labor augmentation. The individual subject will be expected to participate in the study from the time of enrollment until time of discharge from the hospital after delivery.
- ii. Previous work by the principal investigator ([name]) showed that Active Management of Labor, with HDOR as one of its components, reduced the rate of labor dystocia and thus the rate of cesarean delivery, without increasing maternal or neonatal morbidity. This randomized trial was conducted at NMH and recruited 720 patients (75% of eligible women participated in the study) in a 12-month period. Recent hospital data revealed that 3,466 women in the 12-month period prior to the original study proposal would have meet eligibility criteria. As of July 22, 2019, 839women have been enrolled in this study.
- iii. The estimated date for completion of this study including primary analyses of the data is 4 years after the start of the clinical trial. Patient recruitment commenced in September 2015, and we expect to complete primary analyses by November 2019.

Page 6 of 23 Revised Template: November 10, 2014

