- 11.4 Quality Control of Collected Data: Data collection forms will be developed, pretested, and used by the investigators and trained clinical staff to gather baseline and outcome data. Investigator meetings will be held on a quarterly basis, including just prior to the initiation of patient enrollment. After initiation of patient enrollment, investigator meetings will be held monthly for the first three months to discuss any questions regarding the protocol, and also as needed thereafter. Data will be extracted from the electronic medical record system, and investigators and clinical staff will remain blinded to group assignment during the data collection process. Every effort will be made to maintain high quality data; as such, institutional resources REDCap and NITRO Study Tracker will be used for data entry and monitoring.
- 11.5 Describe how data and specimens will be handled study-wide:
 - i. Clinical data that is pertinent to the study endpoints will be extracted from the medical record of each subject (see 'data collection' form) and will be recorded on a standard data collection form. Once all data collection forms and medical charts have been reviewed, all identifiers and protected health information will be removed and research data will be stored and archived in a de-identified manner. The identifiable data will be permanently discarded by permanently deleting the password protected encrypted database with patient identifiers at the earliest opportunity.
 - ii. Data will be stored in accordance with Northwestern University Information Technology (NUIT) File Sharing Policy using SharePoint and Northwestern file servers, which are available for storing and sharing sensitive research data in order to maintain confidentiality and privacy. Only the study investigators who are on the Authorized Personnel list of the IRB approved protocol will be granted access to the research data.
 - iii. Research data will be retained and stored for a minimum of three years after the conclusion of the study as per the Northwestern University Policy. However, research data will be kept for as long as deemed necessary to protect any intellectual property resulting from the work. The research data will be stored and archived in a de-identified manner in accordance with NUIT File Sharing Policy.
 - iv. Only the study investigators who are on the Authorized Personnel list of the IRB approved protocol will be granted access to the research data.

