14.0 Risks to Subjects*

14.1 Currently, both dosing regimens compared in this study (LDOR and HDOR) are approved by established protocols for clinical practice for labor augmentation at NMH. However, reasonably foreseeable risks include increased rates of tachysystole and cesarean deliveries performed for fetal heart rate tracing indications in the HDOR group, increased rates of maternal postpartum hemorrhage and intrauterine infections as well as increased cesarean deliveries performed for labor dystocia in the LDOR. Reasonably foreseeable inconveniences to the subjects include longer labor durations in the LDOR group and increased labor pain in the HDOR group. The protocol has been designed to minimize risks to the subjects and their neonates, regardless of whether they are randomized to LDOR or HDOR

Page 15 of 23 Revised Template: November 10, 2014

- groups. All subjects will sign a form indicating her free and informed consent to participate in the study prior to randomization. Given randomization of dosing regimens that already have well-established safety profiles, we expect a low likelihood of adverse outcomes.
- 14.2 Investigators will be required to report any suspected or actual Unexpected Adverse Events (UAE) that may occur during study participation. UAEs will be defined as any event that meets the following conditions: the event is **not** a known or reasonably foreseeable risk associated with the study procedures (e.g. risks related to administration of oxytocin and confidential information specified in the informed consent), and the event, in the investigators' opinion, is or could be directly related to the subject's participation in this research protocol. Events that are the result of a natural progression of an underlying disease, disorder, condition, or a predisposing risk factor profile for the subject do not qualify as UAEs. The investigators will be responsible for complying with IRB requirements for reporting of UAEs. However, since both dosing regimens compared in this study (LDOR and HDOR) have already been in clinical use for labor augmentation at NMH, we anticipate a low likelihood of UAE.

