- 14.3 The study will only include pregnant women (see Section 16), and thus potential risks to their fetuses will be considered. Several measures of neonatal morbidity have been predefined as safety endpoints in the study. However, based on prior work¹⁰ showing no increase in neonatal morbidity in women assigned to active management of labor using HDOR compared to traditional management, we anticipate no increased risks to fetuses in the proposed study.
- 14.4 Based on the randomized nature of the study, we expect that the risk of discrimination based on demographic factors will be minimal. Subjects will only participate in the study during their hospital stay for labor and delivery, and thus we do not anticipate risks to others who are not subjects.

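### Section 9.4 stops data collection at the woman's discharge, so NICU length of stay, NICU stay over 48 hours and later in-hospital neonatal events can be cut off

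*Combined protocol and SAP*

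**What the plan says.** Section 9.4 states "There will be no long-term follow-up; the study period begins at randomization and ends with discharge from hospital following delivery", and then "Data will be collected only up until time of each subject's hospital discharge". Section 7.1 i likewise has the individual subject take part "until time of discharge from the hospital after delivery".

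The subject is the enrolled woman. Section 3.3 ii says "Our study will only include subjects who are adults", 14.3 says "The study will only include pregnant women", and 14.1 names the two separately in its aim to "minimize risks to the subjects and their neonates".

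The data source is tied to her as well. Section 9.3 iii says "The medical record of each subject's hospital stay will be reviewed and used to collect data", and 11.5 i says "Clinical data that is pertinent to the study endpoints will be extracted from the medical record of each subject". The permission in 25.3 is for access to the subjects' own electronic records during their stay.

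The neonatal outcomes carry no end date of their own. Section 1.1 iii puts a NICU admission of more than 48 hours into the neonatal composite. Section 8.2 lists NICU admission with length of stay, stillbirth or neonatal death, encephalopathy, seizure, cooling and sepsis.

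**The concern.** A neonate in intensive care may remain in hospital after the mother goes home. If collection ends when she leaves:

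- NICU length of stay is recorded only up to her discharge whenever she leaves first.
- NICU stay over 48 hours cannot be confirmed if she leaves before 48 NICU hours have passed.
- A death, seizure or sepsis later in the same neonatal admission goes unrecorded.

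This matters because 1.2 hypothesises no significant difference in neonatal morbidity. Events lost about equally in both arms leave the risk ratio roughly unchanged, but they shrink the absolute difference and the power. A non-significant result then becomes easier to obtain. A truncated NICU stay is partly a measure of how long mothers stay, and the longer the true stays, the more this is so.

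Several outcomes are not at risk: cesarean delivery, cesarean for nonreassuring fetal status, cord gases, five-minute Apgar score, stillbirth, and NICU admission that occurs before she leaves.

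**Working it through.** **The plan's own figure.** The only sample-size figure is for cesarean delivery (11.2 and 23.0): 20% versus 13.4%, two-sided alpha 0.05, 80% power. With a pooled-variance chi-square formula and p̄ = 0.167,

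n = [1.960·√(2·0.167·0.833) + 0.842·√(0.2·0.8 + 0.134·0.866)]² / 0.066² = 500.1, so 501 per group and 1002 in total.

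This reproduces the plan and is not touched by this point. The plan gives no such figure for any neonatal endpoint.

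**Inputs that must be assumed.** The documents give no maternal stay, NICU stay or neonatal event rate, so everything below is illustrative. NICU entry is at birth, and NICU stays are exponential with mean m. Mothers leave at 2 days after vaginal delivery or 4 days after cesarean. The cesarean share is 20% (the plan's LDOR rate).

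**NICU length of stay.** A stay cut at D days has recorded mean E(D) = m(1 − e^(−D/m)). The overall recorded mean is 0.8·E(2) + 0.2·E(4).

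| True mean (d) | E(2) | E(4) | Recorded mean (d) | Share of true |
|---|---|---|---|---|
| 2 | 1.26 | 1.73 | 1.36 | 68% |
| 3 | 1.46 | 2.21 | 1.61 | 54% |
| 5 | 1.65 | 2.75 | 1.87 | 37% |
| 7 | 1.74 | 3.05 | 2.00 | 29% |

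A true difference of 5 versus 7 days would be recorded as 2.00 − 1.87 = 0.13 day, and 3 versus 5 days as 1.87 − 1.61 = 0.26 day.

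**Neonatal composite (1.1 iii).** Let f be the share of composite events identifiable only by NICU over 48 hours or another late item. Let s be the share of vaginally delivered mothers who leave too early for it to be recorded. With full capture after cesarean, the captured share is q = 1 − f·0.8·s. The case s = 1 matches the 2-day assumption above, since a stay that starts at birth cannot exceed 48 hours by day 2.

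Power = Φ{[|p₁ − p₂|·√501 − 1.960·√(2p̄(1 − p̄))] / √(p₁(1 − p₁) + p₂(1 − p₂))}, at recorded rates of 5%·q and 10%·q.

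| f | s | q | Recorded difference (points) | Power |
|---|---|---|---|---|
| none lost | – | 1.00 | 5.0 | 85.3% |
| 0.10 | 0.25 | 0.98 | 4.9 | 84.5% |
| 0.10 | 1.00 | 0.92 | 4.6 | 82.0% |
| 0.30 | 0.25 | 0.94 | 4.7 | 82.9% |
| 0.30 | 0.75 | 0.82 | 4.1 | 77.2% |
| 0.30 | 1.00 | 0.76 | 3.8 | 73.8% |

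Over the same grid, 3% versus 6% goes from 63% to between 62% and 51%, and 8% versus 16% from 97% to between 97% and 92%.

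**Difference between arms.** If HDOR has 13.4% cesareans rather than 20%, slightly more HDOR mothers leave early. For equal true composite rates of 5%, the spurious difference is 0.05·f·s·(0.866 − 0.80). At f = 0.30 and s = 1 this is 0.05·0.30·0.066 = 0.10 percentage point, or 0.5 event per 501. For NICU stay, recomputing with weights 0.866 and 0.134 lowers the recorded mean by 0.03 to 0.09 day.

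**The case against.** The best reply is that 9.4 is loosely drafted and not a deliberate cut-off. Read with full strictness, the passages on data source and record access would bar opening any neonatal chart, yet the protocol plainly means to collect neonatal outcomes. Section 9.4 itself promises data pertinent to the endpoints, and NICU length of stay is one of them. Its second sentence does not say whose discharge ends the study period. Section 11.3 names wider sources (patient records, care providers and subjects), 11.4 names the electronic record system, and the data collection form may already record the neonate's full stay. The trial was also never powered for a neonatal endpoint, so the power figures measure loss against assumed targets.

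Much of this stands. Actual loss is not shown, and what the form records is unknown. But the last sentence of 9.4 contains both a limiting word and an explicit reference to each subject. The wider sources say where data come from, not when collection stops. If the form goes further than 9.4, the two conflict and 9.4 still needs correcting.

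A reader might infer more: that neonatal safety data have already been lost, or that the cut-off biases the comparison between arms. The documents support neither. The form is not visible, and the cut-off applies to both arms. The between-arm artefact is negligible for the composite and under 0.1 day for NICU stay. Nor does the point reach events after the neonate goes home, which the in-hospital design leaves out by choice.

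**Conclusion.** The point holds for the text as written: a stated rule on the end of data collection does not fit several listed neonatal endpoints. It should be fixed, but it does not threaten the primary comparison.

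The material effect falls mainly on NICU length of stay, a secondary safety item. Under the assumptions above, 29% to 54% of a true mean of 3 to 7 days would be recorded; at a true mean of 2 days, 68% would be. For the composite at 5% versus 10%, power falls from 85.3% to between 84.5% and 73.8%, a loss of about 1 to 12 percentage points. The true size is unknown and could be nil if the form already follows the neonate. Confidence is medium for that reason.

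**What to change.** Amend 9.4 and 7.1 so that maternal data end at maternal discharge. Abstract the neonatal endpoints in 1.1 iii and 8.2 from the neonate's chart to the neonate's own discharge, transfer or in-hospital death, identically in both arms and before the code is broken (11.1). Record stays that end in transfer, or are ongoing at data lock, as incomplete; NICU over 48 hours can still be classified once 48 hours have passed. If the data collection form already sets this rule, correct 9.4 to match it.

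Apply this also to women already enrolled (839 by July 2019, per 7.1 ii), where consent and IRB approval allow access to the neonatal record; 25.3 should say so. It must be finished before identifiers and dates are deleted under 10.1 and 11.3, because afterwards the charts may not be traceable.

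The cost is modest chart abstraction by existing staff at the same hospital, with no added visits or procedures, and possibly an IRB amendment. If 5% to 10% of neonates enter the NICU (an assumption), that is about 50 to 100 charts of 1002, of which about 42 to 84 belong to the 839 women already enrolled. Deletion of identifiers waits until this is done.
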